The analysis of this data involves the use of a multiple imputation technique on a transformation of this data. See Section 5.5: Handling of Missing, Unused, and Spurious Data. This is the primary analysis for the PROPEL study.

The primary analysis will be repeated as a sensitivity analysis with the following alternative imputations:

- Standard uninflated imputation (excluding regular post-PROPEL bleeds).
- Imputed bleeds with the mean inflated by 10%.
- Imputed bleeds with the mean inflated by 20%.
- Imputed bleeds with the mean inflated by 40%.
- Imputed bleeds with the mean inflated by 80%.
- Worst case bleed imputation (See Section 5.5: Handling of Missing, Unused, and Spurious Data).

The proportion of subjects with total ABR <2, spontaneous ABR <2, Spontaneous ABR = 0, spontaneous AJBR <2 and spontaneous AJBR = 0, for the second 6-month period (ObsDay 183 to ObsDay364) as well as the full 12-month period treatment period (ObsDay 1 to ObsDay 364), will be analyzed in the same manner as the primary efficacy outcome. The sensitivity analysis described above for the primary efficacy outcome, will not be applicable to the secondary efficacy outcomes.

The total ABR, injury related ABR, spontaneous ABR and spontaneous AJBR, will be analyzed using a generalized linear model fitting a negative binomial distribution with logarithmic link function for the second 6-month period (ObsDay 183 to ObsDay 364) as well as the full 12-month observation period (ObsDay 1 to ObsDay 364). Separate Negative Binomial models will be used for these two time periods. The model is to include the treatment arm assigned (low level or high level), Stratum and race as fixed effects, age at baseline as continuous covariate and the logarithm of the OPE in years as an offset. The following SAS[®] code can be used to perform the analysis:

```
Proc Genmod Data = <Dataset>;
```

```
Class <Treatment> <Strat> <Race> (param=ref ref=first);  
Model <Bleeds> = <Treatment> <PREABR> <Baseline_age> <Race> / type3  
dist = negbin link = log offset = <log_OPE>;  
lsmeans <treatment> / bylevel om CL;  
ODS OUTPUT LSMEANS = <Outdata>;  
Run;
```

where <Dataset> refers to the input dataset, <Treatment> the assigned treatment arm, <STRAT> to the Stratum category, <Race> to the subject's race, <Bleeds> the number of bleeds during the observation period, <Baseline_age> to the subject's age at baseline, <log_OPE> the logarithm of the OPE in years and <Outdata> the output dataset containing the inferential statistics to be presented in the summary tables. Point estimates and confidence intervals obtained from the generalized linear model should be anti-logged prior to presentation.

A multiple imputation technique will be used for incomplete observation periods in the same manner as utilized for the primary analysis (See Section 5.5: Handling of Missing, Unused, and Spurious Data). This is the secondary analysis for the PROPEL study.

The potential correlation between ABR and the pre-infusion average FVIII trough levels as well as the average of the TGA trough results (lag time, time to peak thrombin generation, peak thrombin generation and ETP) will be assessed using linear regression plots with 95% confidence bands and the Spearman rank correlation coefficient for the first 6-month treatment period (ObsDay 1 to ObsDay 182), the second 6-month study treatment period (ObsDay 183 to ObsDay 364) and overall (The full 12-month period [ObsDay 1 to ObsDay 364]). As described in Section 9.1: FVIII Activity and TGA Data, FVIII trough levels will be calculated exactly to the end of the subjects' planned infusion interval; however, trough samples collected outside of ± 16 hours of the planned infusion interval, will be excluded. For TGA results, trough levels for each available visit will be included for the calculation of the average by assay if the sample was collected ± 2 hours of the planned infusion interval. Trough levels taken within ± 16 hours of the planned infusion interval will be used for this correlation test.

The following SAS[®] code can be used to perform the analysis:

```
Proc Corr data = <Dataset> Spearman;  
  Var <Parameter1>;  
  with <Parameter2>;  
  title "Correlation coefficients";  
  ODS Output = <Outdata>  
Run;
```

where <Dataset> refers to the input dataset, <Parameter1> the first parameter to be checked for correlation, <Parameter2> the second parameter to be checked for correlation and <Outdata> the output dataset containing the inferential statistics to be presented in the summary tables. Please note that the two variables being checked for correlation must be sorted/ranked from low to high before using the SAS procedure.

Where applicable, the 95% CI on the median will be determined using the distribution-free CI for the 50th percentile from the SAS[®] UNIVARIATE procedure.

The protocol states that for subjects that leave the PROPEL study before completing the full second 6-month period (defined as ObsDay 364), subjects may provide bleeding data for the remaining days up to the end of the full 6-month period (ObsDay 364). There were two subject cases identified which fits this description in PROPEL:

- Subjects transitioning from PROPEL to the Baxalta Continuation study before ObsDay 364.
- Subjects leaving the study before ObsDay 364 but not transitioning to another Baxalta study.

The appropriate file notes have been put in place describing this process. Details of bleed information inclusion into the PROPEL analysis (primary, secondary and exploratory) is given below.

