7.3.1 Efficacy

1. To compare the 2 prophylactic dosing regimens of BAX 855 targeting 2 different FVIII trough levels with respect to the following:
 - The proportion of subjects in each prophylactic dosing arm achieving a spontaneous^{iv} ABR and spontaneous^{iv} joint bleeding rate (AJBR) of 0 in the second 6-month study period
 - The proportion of subjects in each prophylactic dosing arm with a total, spontaneous ABR and AJBR <2
 - The total, spontaneous, and trauma-related ABRs in the 12-month study period
 - The reduction in ABR between the 2 treatment arms and the historical ABR prior to study enrollment
 - The total weight-adjusted consumption of BAX 855 for each prophylactic regimen
 - The joint status using the HJHS and over time
 - Health-related quality of life (HRQoL) and pharmacoeconomic outcomes (including Short form-36 questionnaire [SF-36], EuroQol 5 dimension [EQ-5D], Haemo-SYM, and healthcare resource utilization)
2. To determine the hemostatic efficacy of BAX 855 in the control of bleeding episodes

^{iv} i.e., not trauma-related

3. To evaluate the efficacy of BAX 855 for perioperative management, if surgery is required

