5.5.1 Annualized Bleeding Rate

For all subjects who prematurely discontinued from the study (i.e., before ObsDay 364), and who refuse to provide data on bleeds for the remaining time till ObsDay 364, the number of bleeds (and hence the ABR), will be imputed for the second 6-month period, using Multiple Imputation techniques as described below. The ABR for a subject is calculated as the number of bleeds divided by the observation period under consideration (expressed in years).

The number of bleeds during the missing observation period in PROPEL, will be imputed for subjects taking into account, additional post-PROPEL bleeding information that is provided for the subject. Post-PROPEL bleeding information obtained for a subject (either by the subject or from another BAX 855 study), will be treated as if observed within PROPEL before the imputation procedures.

For simplicity, the imputation process is described below for a single subject (since the imputation will be performed on a subject specific basis), focussing on the period of interest for the primary endpoint (2nd 6-month period). The imputation process is described in step-by-step manner.

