Imputation Period (days) = (Date Corresponding to ObsDay 364 – Imputation Start Date)

Where imputation start date is as defined in section 5.4.2: Extended Observation Period of Efficacy.

- This “imputation period” will be treated/imputed as a Poisson random variate. The following example SAS[®] code can be utilized to obtain an estimate for the Poisson parameter:

```
Data <ImpSet>;  
  Set <Dataset>;  
  
  <Mu> = exp(1*<Intcpt> + <Beta1>*<sStrat> + <Beta2>*<sRace> +  
            <Beta3>*<sBAge> + <Beta4>*<sOB> + <LIP>);  
  Do i = 1 to 1 000  
    <ImpUB> = Ranpoi(1234,mu);  
    Iteration = i;  
    Output;  
  End;  
Run;
```

Where <Impset> represents the resultant dataset containing the 1 000 imputed bleed count values. <Dataset> is the input dataset containing the parameter estimates obtained from fitting the Negative binomial as discussed above and <Mu> our Poisson parameter as defined above. <Beta1>, <Beta2>, <Beta3> and <Beta4> the parameter estimates for <Stratn>, <Racen>, <BAge> and <OB> respectively. <sStratn>, <sRacen>, <sBAge> and <sOB> hold values specific to the subject being imputed, for numeric stratum category, numeric race category, baseline age and observed bleeds from ObsDay92 till last ObsDay for the subject, respectively. <LIP> is the logarithm of the imputation period (days) for the subject being imputed and <ImpUB> is the imputed number of bleeds during the imputation period for the subject.

Step3: Adding of Imputed Values to the Observed Values

The imputed bleed count of the subject is added to the subject’s observed bleed count (i.e. the subject’s observed bleeds after ObsDay 182), to obtain a bleed count for the complete 2nd 6-month period of the subject.

$$\text{Complete period bleeds} = \text{Observed period bleeds} + \text{Bleeds for imputation period}$$

For each subject to be imputed, the 1 000 imputed values will be merged into the full subject dataset, thus creating 1 000 replicates of imputed (complete) data sets (one for each imputation iteration).

Step4: Calculating ABR and Categorization

From this step onward we are working with all the subjects (those imputed and those not needing imputation) in the same dataset (1 000 replicates of them).

ABR is calculated as:

$$ABR = \frac{(Observed\ Number\ of\ bleeds + Imputed\ number\ of\ bleeds)}{Period\ under\ consideration\ in\ years}$$

Where period under consideration is:

- 1 year (365.2425 days) when working with the full year.

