- 0.5 years (182 days) when working with the second 6-month period.

For presentations using unimputed ABR:

$$Unimputed\ ABR = \frac{Number\ of\ bleeds\ observed\ within\ PROPEL}{Period\ under\ consideration\ in\ years}$$

A numeric categorical variable for imputed ABR during the complete planned treatment period will be derived as follows:

- Category 1: ABR = 0.
- Category 2: ABR > 0.

Step5: Analysis of Imputed Data Sets

Chi-squared statistics with continuity correction should be calculated for each of the thousand complete datasets on the ABR categorical variable with treatment arm as fixed effect. The following SAS® code can be used:

```
Proc Freq Data = <Dataset>;  
  By <Iter>;  
  Tables <ABRCat>*<Trt> / chisq alpha = 0.05 relrisk riskdiff expected;  
  exact or;  
  Ods Output Chisq = <Outdata>;  
Run;
```

Where <Dataset> is the input dataset containing the 1 000 iterations of the completed

data, <Iter> the iteration number, <ABRCat> the numeric ABR category variable, <Trt> the treatment arm and <Outdata> the output dataset containing the continuity adjusted chi-squared statistics.

Step6: Combining of Statistical Results

An approximately Gaussian test statistic will be derived as the square root of the chi-squared statistic with continuity correction and 1 degree of freedom, with the sign set according to the direction of the effect (proportion higher in treatment arm one [High level] than in treatment arm two [Low level]; zero if equal). That is, if the risk difference of the High Level Arm minus the Low Level arm provided by SAS[®] is larger than naught then the sign to retain will be positive and vice versa.

This needs to be done so the requirements of Rubin's rules are met and the SAS procedure PROC MIANALYZE can be used.

The resultant 1 000 approximately Gaussian test statistics will be summarized using the SAS[®] procedure MIANALYZE. SAS[®] code similar to the below can be utilized:

```
Proc MIanalyze data=<Dataset>;  
  Modeleffects <NormStat>;  
  Stderr <NormSterr>;  
  Ods Output ParameterEstimates = <Outdata>;  
Run ;
```

Where <Dataset> represents the input dataset containing the approximately Gaussian statistics, <NormStat> and <NormSterr> the approximately Gaussian statistics and standard error of 1 respectively and <Outdata> the output dataset containing the overall estimate, 95% confidence interval and corresponding P-value.

Step7: Back Transformation

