5.5.1.3 Secondary Endpoint Imputation

For spontaneous bleeds, traumatic bleeds and spontaneous joint bleeds during the 2nd 6-month period, the same procedure as described for the primary endpoint imputation will be applied in separate models.

For bleeds during the full 12-month period, a similar imputation procedure will be applied with the difference being that no restriction on bleeds such as having to be after ObsDay 182 will be made.

The same procedure will be used to impute spontaneous bleedings, traumatic bleedings, and spontaneous joint bleedings in separate models.

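### Should the second-6-month ABR <2 proportions be removed because they equal the ABR = 0 proportions?

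*SAP*

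**What the plan says.** SAP 7.1.2 (Bleeding Episodes) names the secondary responder proportions: "The proportion of subjects with total ABR <2, spontaneous ABR <2, Spontaneous ABR = 0, spontaneous AJBR <2 and spontaneous AJBR = 0". It assigns them to two windows, "for the second 6-month period (ObsDay 183 to ObsDay364) as well as the full 12-month period treatment period (ObsDay 1 to ObsDay 364"), and says that they "will be analyzed in the same manner as the primary efficacy outcome". That means multiple imputation followed by the continuity-corrected chi-square test.

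SAP 5.5.1 defines the rate: "The ABR for a subject is calculated as the number of bleeds divided by the observation period under consideration (expressed in years"). Step 4 of SAP 5.5.1.1 then fixes the divisor for each window: "1 year (365.2425 days) when working with the full year" and "0.5 years (182 days) when working with the second 6-month period". SAP 7.1.2 derives AJBR in the same way as ABR. SAP 5.5.1.3 says of spontaneous, traumatic and spontaneous joint bleeds that "the same procedure as described for the primary endpoint imputation will be applied in separate models".

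The protocol's objective (Protocol 7.3.1) reads: "The proportion of subjects in each prophylactic dosing arm with a total, spontaneous ABR and AJBR <2". It gives no period. The neighbouring objective, for spontaneous ABR and AJBR of 0, is tied to the second 6 months. The SAP is therefore what carries the <2 cut-off into that window.

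**The concern.** Protocol 7.3.1 lists a rate of 0 and a rate below 2 as separate objectives, so a reader expects <2 to be the more lenient criterion. If the two coincide in one of the analysis windows, the report shows the primary result a second time under a secondary heading, and likewise for spontaneous bleeds and spontaneous joint bleeds. Someone who has not done the division could take agreement between the two rows as support at a softer threshold, when it is the same classification under another label. SAP 5.8 (changes from the protocol) does not mention the overlap and SAP 5.14 treats multiplicity as not applicable, so the SAP text gives no warning.

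**Working it through.** **The plan's own figure first.** SAP 2.3 gives 48 per arm for 40% vs 70% bleed-free at two-sided 5% and 80% power. The usual formula with continuity correction gives 49 per arm (42 without correction). Exact binomial power of the continuity-corrected chi-square at 48 per arm is 80.05%. The sample size rests on the = 0 endpoint and reproduces, and nothing below touches it.

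**Inputs**
- Window: ObsDay 183 to 364 (SAP 3.1.1 and 7.1.2; also Day 183 to 364 in Protocol 14.3.1 and 14.4.1), so 364 − 183 + 1 = 182 days.
- Divisors: 0.5 years for the second 6 months and 1 year for the full period (SAP 5.5.1.1 Step 4).
- Bleeds are counts, and imputed bleeds are Poisson draws (SAP 5.5.1.1 Step 2), so every total k is an integer.

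**Second 6 months: ABR = k / period in years**
- k = 0: 0 / 0.5 = 0.
- k = 1: 1 / 0.5 = 2.000, not below 2.
- k = 1 with the exact day count: 365.2425 / 182 = 2.007.
- k = 1 with 181 days (the SAS description in SAP 7.1.2 says ObsDay 363): 365.2425 / 181 = 2.018.
- k = 1 with a shorter personal observation time, for example 120 days: 365.2425 / 120 = 3.04.

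One bleed falls below 2 only if the divisor exceeds 365.2425 / 2 = 182.62 days, and the window holds 182. Surgery does not lengthen it, because SAP 5.3.3 subtracts surgery days from the ObsDay count. So ABR <2 and ABR = 0 both mean zero bleeds, and the same holds for spontaneous ABR and spontaneous AJBR.

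**Full 12 months**
- k = 1: 1 / 1 = 1.000 (365.2425 / 364 = 1.003), below 2.
- k = 2: 2 / 1 = 2.000 (2.007), not below 2.

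Here <2 means at most one bleed and differs from = 0.

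**Simulation.** In 1,000 simulated datasets of 116 integer counts, the two classifications disagreed 0 times with the 0.5-year divisor and 26,766 times with the 1-year divisor.

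**Effect of imputation.** SAP 5.5.1.3 separates the models by bleed type, not by cut-off. Within a type the two criteria are read from the same imputed counts, and the example code fixes the random seed. If the draws were regenerated for each cut-off, the results would differ by Monte Carlo noise only.

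**Illustration on one complete table.** Take 19 of 48 vs 34 of 48 bleed-free, close to the planned 40% and 70%. The continuity-corrected chi-square is 96 × (|19×14 − 34×29| − 48)² / (48×48×53×43) = 96 × 672² / 5,250,816 = 8.256, p = 0.0041. The table for total ABR <2 has the same four cells, so it gives the same result.

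**What deletion would change.** Second-6-month comparisons: 6 planned, 3 distinct. After deletion: 3 reported, 3 distinct, with the same estimates and p-values.

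**The case for a change.** The best case for acting is that the redundancy is certain, can be shown in one line and would cost one line to remove. Since the protocol gives no period for <2, keeping only the 12-month versions would lose no information and would stop the primary result appearing again as a secondary finding. The facts in that argument stand. What does not follow is a benefit to the analysis: no number changes. SAP 5.14 sets no multiplicity procedure, so no alpha is spent on the repeats, and identical counts in adjacent rows are visible to anyone reading the table. Table layout is left to the Output Templates, which are not among the documents, so a footnote can be added there, or in the report, without amending the SAP. Whether one is already planned cannot be checked.

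A second argument is to replace the 6-month cut-off with a real softer responder, such as at most one bleed in ObsDay 183 to 364. That is a new endpoint and not a correction, and it would be looser than the 12-month cut-off. Assuming Poisson counts, a constant rate and 40% bleed-free at 6 months, the 6-month mean is −ln 0.4 = 0.916. The probability of at most one bleed in 6 months is then 0.4 × 1.916 = 77%, against 0.16 × 2.833 = 45% for 12-month ABR <2. Reasonable statisticians could differ on wanting it.

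In the other direction, the identity might be questioned. Protocol 11.1 describes the second period as running from the 6-month visit to the completion visit. With visits at 26 (±1) and 53 (±1) weeks that is nominally 27 weeks (189 days) and at most 29 (203 days). One bleed would then give 365.2425 / 189 = 1.93 or 365.2425 / 203 = 1.80, both below 2. That wording does not govern the analysis: Protocol 14.3.1 and 14.4.1 and SAP 3.1.1, 5.5.1.1 and 7.1.2 all fix the 182-day window.

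**Conclusion.** The arithmetic holds: in the second 6 months, three of the six planned proportion comparisons are exact repeats of the other three. It rests on the fixed ObsDay 183 to 364 window, a divisor of no more than 182.62 days and integer counts, all of which the SAP's definitions supply. Identical printed p-values further assume that the same imputed datasets serve both cut-offs.

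No change to the plan is called for, because there is nothing to gain. Type I error, power, the primary analysis and every distinct estimate are the same with or without the repeats, and the 12-month analysis, where <2 means at most one bleed, still answers the protocol's <2 objective. When the results are read, the second-6-month <2 rows should be taken as restatements of the = 0 rows and not as additional evidence.

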5.4 Observation Periods and Annualized Bleeding Rate

Two types of observation period will be defined for use within the analysis and reporting of this study namely the observation period of efficacy (OPE), and the extended observation period of efficacy (eOPE).

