5.4.1 Observation Period of Efficacy

- The observation period for efficacy (OPE) measured in days, is calculated as:

$$OPE(days) = Observation\ day\ of\ last\ BAX\ 855\ Prophylactic \\ /IR\ Treatment + Last\ Assigned\ Infusion\ Frequency\ (days)$$

Where last assigned infusion frequency is the last dosing frequency assigned to the subject under a dose change or, in the absence of any dose changes, it is the assigned dose frequency at the start of the study.

- The OPE in (years) is calculated from the OPE (days) as:

$$OPE(years) = \frac{OPE(days)}{365.2425}$$

- The OPE (weeks) is calculated from the OPE (days) as:

$$OPE(weeks) = \frac{OPE(days)}{7}$$

- The OPE (months) is calculated from the OPE (years) as:

$$OPE(months) = OPE(years) \times 12$$

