5.4.2 Extended Observation Period of Efficacy

The protocol requires that for subjects that did not complete the full 364 observation days, this study should also include any post-discontinuation (post-PROPEL), bleed information provided by either the subject, or from another BAX 855 study, to augment the bleed data for the subject's missing observation period in PROPEL. To facilitate the use of this post-PROPEL data in the efficacy analysis, the extended observation period of efficacy (eOPE) is defined:

- The eOPE measured in days, is calculated as:

$$eOPE(days) = OPE(days) + (Imputation\ Start\ Date - Stop\ Date\ of\ post-PROPEL\ bleed\ data)$$

Where Stop Date of post-PROPEL bleed data is defined as the minimum of:

- Date corresponding to subject's ObsDay 364 in the PROPEL study.
- Actual recorded date of the last bleed data provided for the subject as post-PROPEL bleed data.

Imputation start date is defined as the maximum of:

- The day immediately following the date corresponding to OPE (days).
- The day immediately following the stop date of post-PROPEL bleed data.
- Date corresponding to subject's ObsDay 183.

- The eOPE in (years) is calculated from the eOPE (days) as:

$$eOPE(years) = \frac{eOPE(days)}{365.2425}$$

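### The second-6-month negative binomial ABR model offsets a 182-day count by whole-study exposure, so its LS-mean ABRs print at about half the true rate

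*SAP*

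**What the plan says.** SAP 7.1.2 analyses total, injury-related and spontaneous ABR and spontaneous AJBR with a log-link negative binomial model, once for ObsDay 183-364 and once for ObsDay 1-364. A single specification serves both windows: arm, stratum and race as fixed effects, with "age at baseline as continuous covariate and the logarithm of the OPE in years as an offset". The sample code uses one log-OPE variable. Of the output, the SAP says: "Point estimates and confidence intervals obtained from the generalized linear model should be anti-logged prior to presentation". It names this the study's secondary analysis.

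SAP 5.4 states: "Two types of observation period will be defined for use within the analysis and reporting of this study". These are OPE and eOPE. OPE (5.4.1) is the observation day of the last prophylactic or recovery infusion plus the last assigned dosing interval. Observation days count from the first PK-guided prophylactic infusion (5.3.1, 5.3.3), so OPE covers the whole study. eOPE (5.4.2) adds follow-up after PROPEL to that same quantity.

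For subject-level ABRs the denominator depends on the window. SAP 5.5.1 divides by the length of the period being analysed, and Step 4 of 5.5.1.1 sets it at one year for the full year and "0.5 years (182 days) when working with the second 6-month period".

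On incomplete follow-up, 7.1.2 says of these models: "A multiple imputation technique will be used for incomplete observation periods in the same manner as utilized for the primary analysis". Bleeds reported after a subject leaves PROPEL are treated as observed (7.1.2.1, 7.1.2.2). Protocol 14.4.2 also calls for separate models for the two windows but names no offset.

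**The concern.** In a log-link count model the offset is the denominator of the rate. The ObsDay 183-364 model counts bleeds over 182 days and divides by roughly a year, so the SAP yields two conflicting ABRs for one period: one from the model and one from its own subject-level rule. Four reported outcomes carry the error, and they would overstate bleed control in both arms.

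There is a second mismatch. For a subject who leaves early, post-PROPEL or imputed bleeds bring the count up to ObsDay 364, but the offset still ends one interval after the last infusion. That affects both models, and in the 12-month model it inflates the rate.

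**Working it through.** **Inputs**
- Count windows: ObsDay 183-364 = 182 days; ObsDay 1-364 = 364 days (SAP 7.1.2).
- Days per year: 365.2425 (SAP 5.4.1).
- Completion visit at 53 ± 1 weeks, that is 364 to 378 days (Protocol 8.2), with an infusion given at that visit (Protocol 21.2).
- Dosing interval 2 days or 3.5 days (Protocol 8.7.5). Some subjects will have other intervals.

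**The plan's own denominator.** 182/365.2425 = 0.498 years, which agrees with the 0.5 years in SAP 5.5.1.1.

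**What the model returns.** If the true annual rate is λ, the expected 182-day count is λ × 182/365.2425. Dividing by OPE/365.2425 gives λ × 182/OPE. The printed rate is therefore the true rate times 182/OPE, or times 364/OPE in the 12-month model, with OPE in days.

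**Completers.** OPE runs from 364 + 2 = 366 to 378 + 3.5 = 381.5 days.
- ObsDay 183-364: 182/366 = 0.497 to 182/381.5 = 0.477. A true ABR of 2.0 prints as 0.99 to 0.95.
- ObsDay 1-364: 364/366 = 0.995 to 364/381.5 = 0.954.

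**Early leavers, count completed to ObsDay 364**

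| OPE (days) | 182/OPE | 364/OPE |
|---|---|---|
| 100 | 1.82 | 3.64 |
| 182 | 1.00 | 2.00 |
| 200 | 0.91 | 1.82 |
| 240 | 0.76 | 1.52 |
| 300 | 0.61 | 1.21 |

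In the second-6-month model the error reverses for anyone leaving before ObsDay 182.

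**Arm level, ObsDay 183-364, by simulation.** Assumptions not taken from the documents: true ABR 3.0 (low arm) and 1.5 (high arm), dispersion 1, and the leaving times shown. There were 58 subjects per arm and 400 runs. In set A, completer OPE is uniform on 364-378 days. In set B, the last infusion is on day 364-374 plus 3.5 or 2 days; set B figures are medians, as some fits gave convergence warnings.

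| Set | Leave early, low/high | Leaver OPE | LS means, SAP offset | LS means, matched offset | Arm ratio, SAP vs matched |
|---|---|---|---|---|---|
| A | none | - | 1.45 / 0.74 | 2.96 / 1.50 | 0.508 vs 0.508 |
| A | 10% / 10% | 183-330 | 1.50 / 0.75 | 2.94 / 1.47 | 0.500 vs 0.501 |
| A | 5% / 15% | 183-330 | - | - | 0.510 vs 0.491 |
| A | 0% / 20% | 183-330 | - | - | 0.535 vs 0.498 |
| B | none | - | 1.47 / 0.73 | 3.01 / 1.49 | 0.498 vs 0.495 |
| B | 10% / 10% | 30-363 | 1.61 / 0.78 | 3.01 / 1.49 | 0.477 vs 0.489 |
| B | 20% / 20% | 30-363 | 1.71 / 0.82 | 2.98 / 1.45 | 0.486 vs 0.500 |

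Against the assumed truth, the LS means are at about 0.49 with no leavers. With 10% leaving they are at 0.51 (second-half leavers only) to 0.52-0.54 (leavers spread over the year), and with 20% spread over the year at 0.55-0.57. With 5% vs 15% leaving, the arm ratio shifts by 0.510/0.491 = 1.04; with 0% vs 20%, by 0.535/0.498 = 1.07.

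**Arm level, ObsDay 1-364** (set A assumptions): no leavers 2.92 / 1.44 against 2.97 / 1.46 with the matched offset; 10% per arm 3.04 / 1.49 against 2.97 / 1.46.

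**Side check on eOPE.** The formula adds imputation start minus the stop date of post-PROPEL data, and one of the candidate start dates is: "The day immediately following the stop date of post-PROPEL bleed data". With OPE 200 and post-PROPEL data to day 364, the start is max(201, 365, 183) = 365, so eOPE = 200 + 365 - 364 = 201, not 364. As written, eOPE would not repair the leaver offset.

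**The case against.** The strongest reply is that a careful programmer would not code this literally. The key to the sample code ties the bleed count to an observation period, which suggests count and offset were meant to share a window. SAP 7.1.2 sends the ABR derivation back to 5.5.1, where the denominator is right, and the code is offered only as an example. SAP 5.4.2 says eOPE exists so that post-PROPEL data can enter the efficacy analysis, so the authors saw that OPE is too short for leavers. Descriptive ABRs for the same window would expose a twofold gap.

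Some of this stands. Halving follows only if the text is followed, and intent may well have differed. But the offset is stated in the prose as well as in the code. OPE serves as a whole-study duration elsewhere (SAP 6.5, 6.6). Where the SAP wants a window-specific offset it defines one: the imputation model in 5.5.1.1 uses the log of the unobserved period, and the prediction step uses the log of the imputation period. Section 7.1.2 does neither, and no model calls eOPE.

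Two points on the figures are also fair. Completer OPE should include the dosing interval, as it does above; using visit days alone (364-378) gives the same 0.50 to 0.48 after rounding. The leaver results depend on assumed leaving times and on assumed differences between arms: the documents give only an overall drop-out rate close to 10% (SAP 2.3).

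**Conclusion.** The concern holds. As written, the ObsDay 183-364 model prints LS-mean ABRs and confidence limits at about half the true annual rate, in conflict with the SAP's own 0.5-year denominator. The completer factor of 0.48 to 0.50 is arithmetic and needs no assumed bleed rate. The overall factor rises to about 0.51-0.54 with 10% leaving early and 0.55-0.57 with 20%, under the assumed leaving times.

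The scope is limited. The primary endpoint, subject-level ABRs and the ABR = 0 and ABR < 2 proportions do not use this offset. The 12-month model is nearly right for completers (0.95 to 1.00) and wrong only for leavers with completed counts. With equal leaving in both arms, the arm ratio stayed within about 3% of its matched-offset value in the simulations; it shifted by about 4% to 7% when leaving was made unequal. The eOPE error changes no planned result unless eOPE is brought into use. The point should be fixed, but it does not threaten the main comparison.

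**What to change.** In SAP 7.1.2, define the offset separately for each window:
- Counts completed by post-PROPEL data or imputation: log(182/365.2425) for ObsDay 183-364 and log(364/365.2425) for ObsDay 1-364.
- Observed-only (unimputed) rates: the log of the days, in years, on which each subject was actually observed within that window.

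If eOPE is kept, define it as OPE + max(0, stop date of post-PROPEL data - OPE end date). Otherwise remove it.

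The cost is SAP wording and derivation code. No new data are needed.
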